### Statistical Methods

Patient characteristics for this cohort (N=50 receiving HCV+ organ) will be presented with summary statistics for baseline demographics and clinical variables. The SVR12 rate will be presented and 95% CI constructed with the exact test. Mean and standard deviation for on-treatment laboratory values will be presented to analyze safety.

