- co-formulated glecaprevir (300mg)/pibrentasvir (120mg) (MavyretTM) given orally for a duration of 8 weeks post-transplantation.

*In summary:* Patients who receive HCV NAT-negative organs are monitored with HCV VL testing as per usual protocol. HCV treatment is only initiated in patients who seroconvert *and* become NAT-positive.

Targeted physical assessment, vital sign measurements, emergence of adverse events and concomitant medication usage will be assessed at scheduled visits and as needed at the time of any unscheduled contact during the 56 day study period and/or the 365 day post-dosing safety follow-up.

Study visits post-cardiac transplantation will occur on days 0, 1, 3, 7, 14, 28, 42, 56, 70, 84, 112, 140, 224, 280, 365.

Version Date: 7/3/2019

The **screening visit** will take place within an estimated 1-5 months prior to cardiac transplantation. When enrollment is complete the patient's insurer will be contacted to confirm coverage of a pan-genotypic DAA. **Day 0** of this study represents the day of cardiac transplantation, initiation of study drug will begin within 7 days of transplantation. After initiation of therapy, each subject will receive their study drug daily through course completion.

Pre-screening workup

Informed consent for evaluation

Completed education session with RN and MD/NP

Complete medical history

Complete physical exam

Laboratory screening (HCV Ab and VL, HIV, CMP, CBC with differential, Coagulation tests)

ECG monitoring

Quality of life assessment (SF-36)

Baseline testing (day of transplant, day 0)

HCV RNA, CMP, LFTs, CBC with differential, Coagulation tests

Review of concomitant meds

Week 1 (Visits on Day 3, 7)

HCV RNA, CMP, LFTs, CBC with differential

Adverse event reporting

Standard of care post-transplant visit

ECG monitoring

Review of concomitant meds

Week 2 (Day 14)

HCV RNA, CMP, LFTs, CBC with differential

Adverse event reporting

Standard of care post-transplant visit

Review of concomitant meds

Week 4 (Day 28)

HCV RNA, HCV Ab, CMP, LFTs, CBC with differential

Adverse event reporting

Standard of care post-transplant visit

Review of concomitant meds

Week 6 (Day 42)

HCV RNA, CMP, LFTs, CBC with differential

Adverse event reporting

Standard of care post-transplant visit

Review of concomitant meds

Week 8 (Day 56)

HCV RNA, CMP, LFTs, CBC with differential

Adverse event reporting

Standard of care post-transplant visit

Review of concomitant meds

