Quality of life assessment (SF-36)

Week 9, (Day 63); One week post DAA completion

Tacrolimus level (for patients on Mavyret)

Week 10, SVR 2 (Day 70)

HCV RNA, HCV Ab, CMP, LFTs, CBC with differential

Tacrolimus level

Adverse event reporting

Standard of care post-transplant visit

Review of concomitant meds

Week 12, SVR 4 (Day 84)

HCV RNA, CMP, LFTs, CBC with differential

Adverse event reporting

Standard of care post-transplant visit

Review of concomitant meds

Week 16, SVR 8 (Day 112)

HCV RNA, CMP, LFTs, CBC with differential

Adverse event reporting

Standard of care post-transplant visit

Review of concomitant meds

Week 20, SVR 12 Visit (Day 140)

HCV RNA, CMP, LFTs, CBC with differential

Review of concomitant meds

Quality of life assessments (SF-36)

Week 32, SVR 24 Visit (Day 224)

HCV RNA, CMP, LFTs, CBC with differential

Review of concomitant meds

1 year visit (Day 365)

HCV RNA, CMP, LFTs, CBC with differential

Review of concomitant meds

Quality of Life assessment (SF-36)

**Serum pregnancy tests** (for all females of childbearing potential) will be conducted at screening and performed immediately prior to transplantation for all women of reproductive age as a standard of care. Because the effect, if any, of Epclusa™ or Mavyret™ on an embryo or fetus (developing baby still in the womb) is not known, patients may not participate in this study if they are pregnant, breastfeeding, or planning to become pregnant. Females who are able to become pregnant must agree to use adequate birth control use throughout the duration of the study. For the purposes of this study, adequate birth control means one of the following:

1. Intrauterine device (IUD)
2. Condom with spermicide
3. Diaphragm with spermicide
4. Complete abstinence (not having sex at all)

Hormonal forms of birth control including birth control pills, vaginal rings (like NuvaRing), implants (like Implanon), or injections (like Depo-Provera) may not work during treatment with Epclusa™ or

Version Date: 7/3/2019

Mavyret™ and are not on the acceptable forms of birth control list. After patients have been off Epclusa™ or Mavyret™ for at least two weeks, they can again begin to use a hormonal form of birth control.

**Men** enrolled in the protocol must also agree to use adequate contraception while participating in this study. Adequate contraception is:

1. Condom with spermicide, and
2. Female partners must use an approved method of birth control as listed above

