## **VI. Biostatistical Analysis**

### Variables/Time Points of Interest

The primary variable of interest will be HCV RNA at the multiple time-points assessed during and after treatment.

The primary efficacy outcome “Prevention of HCV Transmission” will be determined by a negative HCV RNA test.

The safety outcomes include summation of treatment related adverse events and transplant rejection or patient mortality. On treatment eGFR, proteinuria, hemoglobin, and liver function tests will be summarized to assess safety.

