### **Risks related to transplantation with an HCV infected heart (or heart and kidney)**

#### Liver problems

While unlikely, it is possible that DAAs will not result in the same efficacy following cardiac transplant. If HCV is transmitted and not eradicated it is possible that HCV infection post-transplant could cause health problems, including liver injury. In the short term, infection with HCV can cause a flu-like illness that includes fatigue, nausea, fever, abdominal pain, vomiting, joint pain, and yellowing of the skin (jaundice). Although it is very rare, infection with HCV can cause severe inflammation of the liver or even liver failure, including a condition called fibrosing cholestatic hepatitis. The risk of this complication in patients without HCV who receive a transplant from a donor with HCV is unknown. This complication can be treated and cured in the majority of cases with the HCV medications.

Cirrhosis of the liver can cause someone to experience leg swelling, yellow skin, skin itching, abdominal bleeding, shortness of breath, and the abdomen to fill with fluid (ascites). Liver failure can also cause death. Based on the limited data available, it would be extremely rare for someone in the study to experience liver failure in the first few months after transplantation because the study will be giving HCV treatment right away.

In the unlikely event that the patient develops HCV infection despite DAA therapy, we will be prepared to offer 2nd line treatment using + ribavirin or MavyretTM + ribavirin plus an additional DAA agent. In the unlikely event that this fails, there may be continued inflammation and scarring of the liver that over many years (10-30) that can lead to cirrhosis. If HCV causes cirrhosis, the patient is at increased risk of developing liver cancer, liver failure requiring a subsequent liver transplant, or death. Of note, we anticipate that with study drug treatment, or if necessary additional HCV therapies, we will be able to successfully prevent transmission and eradicate HCV in our study population.

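### Liver, renal and blood-count values after treatment are collected to Day 365 but have no planned analysis, and on-treatment values are reported only as mean and SD

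*Combined protocol and SAP*

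**What the plan says.** Two sentences in Section VI define the laboratory safety analysis. Under Variables/Time Points of Interest: "On treatment eGFR, proteinuria, hemoglobin, and liver function tests will be summarized to assess safety". Under Statistical Methods: "Mean and standard deviation for on-treatment laboratory values will be presented to analyze safety". No other laboratory analysis is described: no post-treatment summary, threshold count, shift table, maximum or change from baseline.

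The remaining safety outcomes carry no on-treatment limit: "The safety outcomes include summation of treatment related adverse events and transplant rejection or patient mortality".

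Section V treats the later period as part of safety. It has adverse events assessed during the "56 day study period and/or the 365 day post-dosing safety follow-up", and its visit list itemises a metabolic panel, liver tests and a blood count at Days 70, 84, 112, 140, 224 and 365. On timing, each drug is "given orally for a duration of 8 weeks post-transplantation" and "initiation of study drug will begin within 7 days of transplantation". The paragraph on achieving SVR plans an extension from 8 to 12 weeks where virus is detected at the end of the course.

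Section VII, Liver problems, names the hazard: "If HCV is transmitted and not eradicated it is possible that HCV infection post-transplant could cause health problems, including liver injury". The next subsection, on additional risks of HCV, lists inflammatory damage to a kidney transplant among problems it calls rare.

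**The concern.** The plan defines a safety follow-up and schedules its blood tests, but the analysis text stops at the end of treatment. HCV that is transmitted and not eradicated is still present after the drug stops. Liver injury from it, or injury to a kidney graft in the heart-kidney recipients that Section III admits, can therefore fall in the part of follow-up whose laboratory results have no analysis.

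Within the treatment window the choice of statistic also matters. Section VII describes severe liver inflammation as very rare, so with at most 50 treated patients the question is whether one or two had it. A mean and SD describe the cohort and do not say how many patients crossed a level of concern, or which.

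At stake is the laboratory part of Aim 2. A report that follows the plan could describe laboratory safety without using any chemistry, liver or blood-count result obtained after the drug stopped.

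**Working it through.** The plan gives no power, event rate or threshold for laboratory safety, so there is no figure of its own to reproduce. The check compares the Section V schedule with the Section VI analysis text.

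**1. When treatment ends.** Start is Day 0 to Day 7 and the course is 8 weeks (56 days).
- Day 0 start: 0 + 56 = Day 56.
- Day 7 start: 7 + 56 = Day 63.
- Both precede Day 70, the first post-treatment laboratory set.

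**2. Itemised post-baseline laboratory sets.**
- Up to Day 56: Days 3, 7, 14, 28, 42, 56 = 6 sets.
- After treatment: Days 70, 84, 112, 140, 224, 365 = 6 sets.
- Share with no planned analysis: 6 / (6 + 6) = 50%.

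Days 1 and 280 are on the visit-day list but have no itemised laboratory set. If both had one, the share would be 7 / 14, still 50%. In a patient started after Day 3, the Day 3 set would also fall outside the on-treatment window; it is not counted here.

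**3. Patients extended to 12 weeks (84 days).** Treatment ends between 0 + 84 = Day 84 and 7 + 84 = Day 91. Days 70 and 84 become on-treatment, and Days 112, 140, 224 and 365 remain outside: 4 / 12 = 33%.

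**4. How few cases to expect.** With N = 50 and an assumed rate p of uneradicated HCV, expected cases = 50p and P(at least one) = 1 − (1 − p)^50.
- p = 1%: 0.5 expected; P = 39.5%.
- p = 2%: 1.0 expected; P = 63.6%.
- p = 5%: 2.5 expected; P = 92.3%.

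These rates are assumptions, since the plan states none.

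**5. What mean and SD show.** Assume 49 patients with ALT mean 25 U/L and SD 10, plus one patient at value v. Mean = (49 × 25 + v) / 50, and SD is the pooled sample SD on 49 degrees of freedom.
- v = 125: mean 27.0, SD 17.3.
- v = 250: mean 29.5, SD 33.3.
- v = 500: mean 34.5, SD 67.9.

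The mean barely moves. The SD does rise and would make a careful reader suspect an outlier, but it gives neither the number of patients affected nor who they are.

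**6. What a count would show.** Patients crossing a prespecified threshold, with exact (Clopper-Pearson) 95% CI:
- 0/50: 0% (0 to 7.1%).
- 1/50: 2% (0.05 to 10.6%).
- 2/50: 4% (0.5 to 13.7%).

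**The case against.** A reader might infer that injury or relapse after treatment is never analysed. The documents do not support that. Adverse events, rejection and mortality are safety outcomes with no on-treatment limit, and viral failure is analysed through SVR12 with an exact interval and through Aim 3 to Day 365. What lacks an analysis is the set of post-treatment laboratory values.

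These other routes only partly fill the gap. SVR12 and Aim 3 measure virus, not organ injury. Only treatment-related adverse events are summed, and hepatitis caused by the donor organ's virus may not be attributed to the drug. Section V says in general terms that adverse events are assessed at scheduled visits, but the itemised lists for Days 140, 224 and 365 contain no adverse-event line.

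Other strong readings also go too far:
- Section VII names HCV that is transmitted and not eradicated, which includes failure during treatment and not only relapse afterwards. Section V gives no purpose for the late blood tests, so they cannot be said to be drawn to detect relapse.
- By calendar time, (365 − 56) / 365 = 85% of the year lies after Day 56. That is a share of days, not of data; by laboratory set the share is half.
- A mean quoted alone exaggerates the masking. With 49 patients at ALT 25 U/L and one at 400 U/L (assumed), the mean is (49 × 25 + 400) / 50 = 32.5, but the SD is about 53. An SD larger than the mean would not pass unnoticed.
- For the kidney, collection itself is incomplete. Section VI lists proteinuria, but no urine protein test is itemised in Section V.
- Nothing suggests that treating clinicians would miss an abnormal result. The gap is in analysis and reporting.

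It can also be argued that Aim 2 concerns safety of the drug, for which an on-treatment window is a recognised choice, and that a pilot of this size does not need a full set of shift tables. Both points have some force. They limit how much to add, but they do not explain collecting six sets under a safety follow-up and assigning them no analysis. Descriptive counts need no power.

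**Conclusion.** The point holds as a gap in the laboratory analysis. Followed as written, Section VI leaves 6 of the 12 itemised post-baseline laboratory sets without any summary for a standard 8-week course, and 4 of 12 for a patient extended to 12 weeks. It counts no patient with a severe abnormality at any time. Organ injury after treatment would enter the safety results only as a treatment-related adverse event, a rejection or a death.

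The set counts rest on the itemised Section V schedule and a start within 7 days of transplant. The ALT figures and failure rates are assumed and only illustrate the behaviour of the statistics. The primary efficacy analysis is unaffected. The change is worth making because it is cheap and bears directly on Aim 2.

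**What to change.** Amend both Section VI paragraphs as follows.
- Summarise eGFR, hemoglobin and liver tests at every itemised visit through Day 365, split into on-treatment and post-treatment by each patient's actual dosing dates. This handles late starts and 12-week extensions without a fixed cut-off day. State how values during any re-treatment are classified.
- Report the number and percent of patients, with exact 95% CI, whose worst post-baseline value crosses laboratory thresholds set before the data are examined, overall and by period.
- List individual values over time for any patient with detectable HCV RNA after treatment.
- Keep mean and SD as a supplement.

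Reconcile proteinuria between Section VI, which lists it, and Section V, which itemises no test for it.

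Apart from proteinuria, the cost is revised wording and a few more tables from blood tests already scheduled. The sample size does not change. Early values will also reflect surgery, so first-week abnormalities need cautious reading; the per-visit and per-period display helps with that.

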### Power/Sample Size:

This is a pilot study. Up to 100 patients will be enrolled (consented for the possible receipt of an HCV-positive organ), the total number of patients eligible to receive transplant and study drug = 50.

## **VII. Risks and Discomforts**

### Psychological risk

Participation in research may result in undesired changes in thought process or emotion (episodes of depression, stress, guilt). Patients may experience discomfort when being asked questions about their medical history that they deem to be private.

### **Risks related to transplantation with an HCV infected heart (or heart and kidney)**

#### Liver problems

While unlikely, it is possible that DAAs will not result in the same efficacy following cardiac transplant. If HCV is transmitted and not eradicated it is possible that HCV infection post-transplant could cause health problems, including liver injury. In the short term, infection with HCV can cause a flu-like illness that includes fatigue, nausea, fever, abdominal pain, vomiting, joint pain, and yellowing of the skin (jaundice). Although it is very rare, infection with HCV can cause severe inflammation of the liver or even liver failure, including a condition called fibrosing cholestatic hepatitis. The risk of this complication in patients without HCV who receive a transplant from a donor with HCV is unknown. This complication can be treated and cured in the majority of cases with the HCV medications.

Cirrhosis of the liver can cause someone to experience leg swelling, yellow skin, skin itching, abdominal bleeding, shortness of breath, and the abdomen to fill with fluid (ascites). Liver failure can also cause death. Based on the limited data available, it would be extremely rare for someone in the study to experience liver failure in the first few months after transplantation because the study will be giving HCV treatment right away.

In the unlikely event that the patient develops HCV infection despite DAA therapy, we will be prepared to offer 2nd line treatment using + ribavirin or MavyretTM + ribavirin plus an additional DAA agent. In the unlikely event that this fails, there may be continued inflammation and scarring of the liver that over many years (10-30) that can lead to cirrhosis. If HCV causes cirrhosis, the patient is at increased risk of developing liver cancer, liver failure requiring a subsequent liver transplant, or death. Of note, we anticipate that with study drug treatment, or if necessary additional HCV therapies, we will be able to successfully prevent transmission and eradicate HCV in our study population.

#### Additional risks of HCV:

HCV can cause other types of inflammation in the body, such as arthritis, rash, anemia, nerve pain and inflammation damage to your kidney transplant. These problems are rare, and affect less than 2% of people who have HCV. These problems should respond to effective HCV treatment.

## **Risks Related to Study Medications**

### Risks of sofosbuvir/velapatasvir (EpclusaTM)

Sofosbuvir/velapatasvir (EpclusaTM) is an FDA approved pan-genotypic regimen for treating HCV infection. Thousands of patients have received this medication for HCV treatment.

In patients receiving EpclusaTM for 8 weeks the most common side effects were fatigue, headache, and nausea (occurring in approximately 1 in 10 patients). Only 0.2% of patients had side effects so severe that they had to stop treatment.

The safety and tolerability of EpclusaTM after cardiac transplantation has not yet been extensively studied. It is possible that taking immunosuppressant medications needed after cardiac transplant may change the effectiveness or side effects of EpclusaTM.

Risks of glecaprevir/pibrentasvir (MavyretTM)

Glecaprevir/pibrentasvir (MavyretTM) is an FDA approved pan-genotypic regimen for treating HCV infection. Thousands of patients have received this medication for HCV treatment.

The adverse reactions data for MavyretTM in subjects without cirrhosis were derived from nine Phase 2 and 3 trials which evaluated approximately 2,300 subjects infected with HCV genotype 1, 2, 3, 4, 5, or 6 who received MavyretTM for 8, 12 or 16 weeks. In patients receiving MavyretTM the most common side effects were headache (13%), fatigue (11%), and nausea (8%). The overall proportion of subjects who permanently discontinued treatment due to adverse reactions was 0.1% for subjects who received MavyretTM for 8, 12 or 16 weeks.

The safety and tolerability of MavyretTM after cardiac transplantation has not yet been extensively studied. It is possible that taking immunosuppressant medications needed after cardiac transplant may change the effectiveness or side effects of MavyretTM.

Risk of allergic reaction

As with any drug, an allergic reaction can occur. Allergic reactions can be mild or serious, and can even result in death in some cases. Common symptoms of an allergic reaction are rash, itching, skin problems, swelling of the face and throat, or trouble breathing.

## **Risks Related to Study Procedures**

Risks of Blood Draws

The patient may have a bruise (a black-and-blue mark) or pain where researchers take the blood samples. There is also a small risk of feeling lightheaded, fainting, or infection. A total of up to 53 tablespoons of blood will be drawn over the course of the entire study.

Risks to an Embryo or Fetus, or to a Breastfeeding Infant

Because the effect, if any, of EpclusaTM or MavyretTM on an embryo or fetus is not known, the patient may not participate in this study if they are pregnant, breastfeeding, or planning to become pregnant. This is not a new requirement necessitated by this protocol, as patients on the cardiac transplant list must also agree to not become pregnant while awaiting and for a period of time after transplantation.

Study Drug Exposure

Patients will not receive the study drug until post-transplant or just prior to their transport to the operating room (OR) to receive a donor organ. We anticipate that the likelihood of a patient not receiving an organ after taking a dose of study drug is extremely low. However, in the event that a patient does receive the initial dose of study drug and not an HCV-positive heart, we would then plan to immediately stop the study drug. No additional study drug would be given unless the patient was again offered an HCV-positive organ and returning to the OR.

## **VIII. Potential Benefits**

Receipt of an organ

Participants may receive a cardiac transplant because they are enrolled in this study. For some patients, they may have not received an organ at all if the severity of their disease would have otherwise led to death while awaiting organ transplant.

Shortened wait time

Participants may spend a shorter duration of time on the transplant waitlist than they otherwise would have if they had not been a part of the research study.

Improved patient quality of life

A heart that would have otherwise gone to waste can potentially be used to prolong the life and significantly improve morbidity for an individual.

Cost Reduction

This procedure could also eliminate costs associated with the management of end stage heart disease and hospitalization.

Increase organ donor pool (an otherwise stagnant number)

This study could increase the number of viable hearts for transplant and greatly reduce the HCV-positive cardiac discard rate.

